#### Storage and Stability

Store at Controlled Room Temperature, 15–30°C (59–86°F). Store in original container, protected from direct sunlight and moisture.

#### 11.0 MEASURES

Before they start treatment and during the course of study treatment, patients will be asked to assess the severity of their hot flashes (descriptions provided in Appendix I) and complete a baseline symptoms determination (Appendix II) (Week 1 only), daily Hot Flash Diaries (Appendix IV), along with weekly Symptom Experience Questionnaires (Appendix V). The Hot Flash Related Daily Interference Scale (HFRDIS) (Appendix VI) will be completed prior to initiation of and at the conclusion of study treatment. All patients will receive weekly phone calls from study staff (Appendix VII) to document compliance with study drug, encourage completion of requisite study questionnaires, collect adverse events and address any patient concerns or problems.

#### 11.1 Baseline Symptom Determination (Appendix II)

The baseline symptoms determination is completed after registration and randomization but prior to initiation of study treatment. This form has patients record the number of total hot flashes they experience on a daily basis, along with the number of hot flashes according to severity (mild, moderate, severe, or very severe) over the first 7 days of the study period. It is estimated that completing the baseline symptom determination will take 3-5 minutes daily. Questionnaires should be returned to the investigator at the end of the baseline week (week 1) and at the end of treatment (i.e., after the 7th week following study entry). The patient should be supplied with two addressed/stamped envelopes for returning the forms.

#### 11.2 International Prostate Symptom Score (IPSS) (Appendix III)

This tool has been added to this study at screening and to be completed at the end of every week of treatment in response to FDA recommendations to ensure that patients do not have urinary retention issues. This is an 8-item scale, widely used in clinical practice, which measures lower urinary tract symptoms. It includes questions encompassing incomplete bladder emptying, frequent urination, urgency, nocturia, intermittency, weak stream, straining, and quality of life related to urinary symptoms[42].

There are robust data to suggest that prostate cancer patients on active surveillance experience significantly decreased urinary health relative to men without prostate cancer. In a cohort analysis of 6,000 community dwelling older men, we observed that compared to men without prostate cancer, men with prostate cancer on active surveillance (i.e. those who had not undergone treatment) reported a significantly diminished quality of life due to urinary symptoms[43].

#### 11.3 Hot Flash Diary (Appendix IV)

The Hot Flash Diary is completed daily during each of the 6 weeks that patients are taking the study treatment. Like the Baseline Symptom Determination, the form has patients report the number and severity of their daily hot flashes. Additionally, it has them report how many doses of the study drug they took on each day. Completion of the Hot Flash Diary is anticipated to take less than a minute per day.

#### 11.4 Symptom Experience Questionnaire (Appendix V)

The Symptom Experience Questionnaire is collected at the end each of the 7 weeks of the study period. This form collects patient reported toxicity and quality of life data using a 0-10 scale, with one question that allows an unstructured response to report symptoms not captured in the questions provided. Estimated completion time for the Symptom Experience Questionnaire is 10-15 minutes each week.

#### 11.5 Hot Flash Related Daily Interference Scale (HRFDIS) (Appendix VI)

Hot Flash Related Daily Interference Scale (HFRDIS), a tool developed by [name].[33] We recently asked 10 men with androgen deprivation hot flashes, to review this tool. All of the HFRDIS items were assessed as clear, appropriate, and easy to interpret. The items related to work and sexuality were identified as potentially difficult to answer if the individual was retired or not sexually active, however all of the men were able to provide a numeric score for these items. We also discussed the above with [name], who developed the HFRDIS tool and have identified other studies that have used the HFRDIS in men receiving androgen deprivation therapy [34-36]. These studies provide additional data supporting the reliability and validity of the 10-item instrument in this population.

The Hot Flash Related Daily Interference Scale is to be completed by all participants at baseline (Week 1) and at the conclusion of the study (Week 7). It will also be completed at the end of Weeks 2 and 4 of study treatment, as it asks questions related to hot flashes over the past two weeks. This 10-item questionnaire uses a 1-10 scale to assess the interference caused by hot flash symptoms with specific aspects of patients' personal lives. Each completion of the HFRDIS is expected to take 5 minutes.

#### 11.6 Nurse Telephone Contact (Appendix VII)

All patients will receive weekly phone calls from study staff, to document compliance with study drug, encourage completion of requisite study questionnaires, and address any patient concerns or problems and assess adverse events. The nurse weekly phone calls will continue during the optional cross over phase, to assess and collect adverse events during this time.

#### **12.0** END OF TREATMENT/INTERVENTION

#### **12.1** Duration of Protocol Treatment

Protocol treatment is to continue for 6 weeks from the time of start of treatment. Please see the study calendar (Section 5.0) and the treatment section (Section 7.0) for treatment and follow up time periods.

#### 12.2 Criteria for Discontinuation of Protocol Treatment/Intervention

In the absence of treatment delays due to adverse event(s), treatment may continue until one of the following criteria applies:

- Disease progression (if applicable)
- Intercurrent illness that prevents further administration of treatment
- Unacceptable adverse event(s)
- Patient decides to withdraw from the study
- General or specific changes in the patient's condition render the patient unacceptable for further treatment in the judgment of the investigator
- Patient non-compliance
- Termination of the study by sponsor
- The drug manufacturer can no longer provide the study agent (if applicable)

The reason(s) for protocol therapy discontinuation, the reason(s) for study removal, and the corresponding dates must be documented in the Case Report Form (CRF).

#### 12.3 Follow-up

#### **12.3.1** Duration of Follow-up

Protocol treatment is to continue for 6 weeks. Please follow the data submission requirements outlined in the study calendar (Section 5.0). There is no further clinical or survival follow up beyond the 6-week study period. For patients who participate in the optional crossover phase, there will be a 6-week follow up.

#### 12.3.2 Follow-up for Patients who Stop Study Treatment Early

Protocol treatment is to continue for 6 weeks. Patients who do not complete 6 weeks of protocol treatment for any reason will still be expected to follow the data submission requirements outlined in the study calendar (Section 5.0) and will thus be followed up until 6 weeks post-randomization.

#### Follow up for patients who stop due to toxicity

If the patient decides to discontinue the study medication because of unacceptable side effects, he is to call the study nurse. The patient should be encouraged to complete diaries/questionnaires to date and send them in. The patient can then be taken off study. The off-study date to be used is either (1) the day after the patient took some study medication OR (2) the day after the patient last recorded some research data on the patient questionnaire--whichever occurred last.

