#### 5.0 STUDY CALENDAR

#### **Pre-study Testing Intervals:**

The pre-study testing intervals are guidelines only. Laboratory and clinical parameters during treatment are to be followed using individual institutional guidelines and the best clinical judgment of the responsible physician. It is expected that patients on this study will be cared for by physicians experienced in the treatment and supportive care of patients on this trial.

When calculating days of tests and measurements, the day a test or measurement is done is considered Day 0. Therefore, if a test were done on a Monday, the Monday one week later would be considered Day 7.

	Prior to Registration	Baseline booklets (Days 1-7)	Daily during treatment (Days 8-49)	End of each week of treatment
Tests & Observations				
History and physical, including Vital signs	Х			
Height, Weight, ECOG PS	X			
Baseline Symptom Documentation ( Appendix II )		X (1)		
International Prostate Symptom Score- (Appendix III)	X			Х
Hot Flash Diary ( Appendix IV )			Х	
Symptom Experience Questionnaire ( Appendix V )		A (1)		Х
Hot Flash Related Daily Interference Scale (HFRDIS) ( Appendix VI )		A (1)		B(2)
Telephone Contact and AE assessment (Appendix VII)				X (2)

**To be completed** ≤ **60 DAYS before registration:** History and physical.

1 Nurse/research coordinator should call the patient, to remind him to send in the baseline questionnaire booklets to the site, which are required to be completed prior to start of study treatment.

- 2 All patients will receive weekly phone calls from study staff (nurse or research coordinator), to document compliance with study drug, encourage completion of patient questionnaires, assess adverse events, and address any patient concerns or problems. They will also remind the patient to return the completed questionnaire booklets. For patients who choose to cross over, nurse phone calls will occur weekly to assess adverse events during the unblinded cross over phase. (See Section 7.3)
- A To be completed on Day 7.
- B To be completed at the end of Weeks 2, 4 and 6 only (Weeks 3, 5 and 7 when measured from registration).

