#### 8.0 DOSE AND TREATMENT MODIFICATIONS, UNBLINDING

#### 8.1 Ancillary Therapy, Concomitant Medications, and Supportive Care

- **8.1.1** Patients should not receive any other treatment or participate in trials which would be considered treatment for hot flashes or impact the primary endpoint. Simultaneous enrollment on other treatment studies is not allowed during the 7 week study period.
- **8.1.2** Patients should receive full supportive care while on this study. This includes blood product support, antibiotic treatment, and treatment of other newly diagnosed or concurrent medical conditions. All blood products and concomitant medications such as antidiarrheals, analgesics, and/or antiemetics received from the first day of study treatment administration until 30 days after the final dose will be recorded in the medical records.
- **8.1.3** Treatment of the patient's cancer should not be influenced by this study. If the patient stops ADT while participating in the study, it should be recorded on the study forms.

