#### 8.2 Dose Modifications

Dose modifications to the patient's cancer treatment are up to the discretion of the treating physician. During participation in the study, if the patient develops any symptoms attributed to the drug that are considered to be of unacceptable severity by the patient and/or physician, oxybutynin/placebo doses will be adjusted as follows:

Dose modifications for adverse events				
Low Dose	Maintain prescribed dose, but decrease frequency from BID to once daily.			
(2.5 mL BID)	If symptoms are still unacceptable by the patient and/or physician, drug will be discontinued and patient will be taken off study.			
High Dose (5.0 mL BID)	If toxicity occurs, decrease dose from 5 mL BID to 2.5 mL BID. If symptoms persist, decrease dose from 2.5 mL BID to 2.5 mL once daily. If symptoms are still unacceptable by the patient and/or physician, the drug will be discontinued and patient will be asked to complete questionnaires to date and then be taken off study.			

**Urinary retention**: For patients on both doses, if at any time during treatment, the patient develops severe urinary symptoms, he should immediately discontinue study treatment and get a post void residual ultrasound assessment as clinically indicated.

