#### 12.4 Extraordinary Medical Circumstances

If, at any time the constraints of this protocol are detrimental to the patient's health and/or the patient no longer wishes to continue protocol therapy, protocol therapy shall be discontinued. In this event:

- Document the reason(s) for discontinuation of therapy on data forms.
- Follow the patient for protocol endpoints as required by the Study Calendar.

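### Sections 8.2, 12.3.2 and 12.4 conflict on whether men who stop study drug for side effects keep giving data, so their week-6 scores may go uncollected

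*Combined protocol and SAP*

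**What the plan says.** **Texts that end data collection.** In the dose-modification table of section 8.2, the last step of the low-dose row reads "drug will be discontinued and patient will be taken off study". The high-dose row reads "the drug will be discontinued and patient will be asked to complete questionnaires to date and then be taken off study". The paragraph of section 12.3.2 on stopping for toxicity says: "The patient should be encouraged to complete diaries/questionnaires to date and send them in. The patient can then be taken off study". Its off-study date is the later of two dates: the day after the last dose, or "the day after the patient last recorded some research data on the patient questionnaire". The phone guide in Appendix VII tells callers that a man who decides to stop the study before week 7 should fill in questionnaires as far as he has got.

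**Texts that continue it.** Section 12.3.2 opens with "Patients who do not complete 6 weeks of protocol treatment for any reason will still be expected to follow the data submission requirements" of the study calendar, and puts the end of follow-up at six weeks after randomization. Section 12.4 covers protocol therapy stopped because the protocol is detrimental to health or because the patient no longer wants it. It says: "Follow the patient for protocol endpoints as required by the Study Calendar". The calendar column holding the hot flash diary has a heading that begins "Daily during treatment (Days 8-49".

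**Analysis.** Section 13.1 sets the primary endpoint at six weeks, by intent-to-treat. Section 13.4 tests the week-6 contrast in a mixed model and says its estimates are unbiased if data are missing completely at random or at random. It plans missing-data summaries by arm and a sensitivity analysis whose assumptions it does not specify. Its responder analyses, for scores and for frequencies, class missing values as non-response.

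**The concern.** Two sites could each follow the protocol and collect different data on the same kind of patient. One takes the man off study under section 8.2, with diaries to the stopping date or with none requested. The other keeps him on the diary to the end of the calendar under the opening of section 12.3.2.

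The weeks at risk include week 6, where the primary contrast is made. A man who leaves stays in the mixed model through the weeks he completed, but his week-6 value is in effect projected from the men who stayed. The responder analyses call the same man a failure. Objective 2.2.3 asks whether these methods agree, so uncollected diaries could produce disagreement that owes nothing to the drug. No later analysis can recover a diary that was never kept.

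**Working it through.** **1. The instructions side by side**

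| Place | Who | Data after stopping | Force |
|---|---|---|---|
| 8.2, low-dose row | symptoms still unacceptable at last step | none requested | directive |
| 8.2, high-dose row | same | questionnaires to date only | directive |
| 12.3.2, toxicity paragraph | man who stops for side effects | to date, then may leave | permissive |
| Appendix VII | man who stops the study early | to that point | instruction to caller |
| 12.3.2, opening | any early stop, whatever the reason | study calendar | expected |
| 12.4 | therapy detrimental or no longer wanted | endpoints per calendar | directive |

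A man at the last step of section 8.2 falls under the first or second row and also under the fifth. He plausibly falls under the sixth. No text ranks them.

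**2. What the calendar asks of him.** The diary column fixes Days 8-49 but ties them to treatment, and section 11.3 describes the diary as completed in the weeks that patients take study drug. Section 12.3.2 sends men who have stopped treatment to that calendar, so it intends them to be covered, but the column and section 11.3 do not say so. The end point is also loose. Section 11.1 puts randomization before the baseline week. Six weeks from randomization is 42 days, and 49 - 42 = 7, so read literally follow-up ends about a week before Day 49.

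**3. The plan's own power figure.** Inputs (section 13.5): 26 per comparison group, standardized difference 0.50, intraclass correlation 0.50, six weekly scores, two-sided alpha 0.10.
- SD of a six-week mean = sqrt((1 + 5 × 0.5)/6) = 0.764
- SE = 0.764 × sqrt(2/26) = 0.212
- 0.50/0.212 = 2.36; 2.36 - 1.645 = 0.715; power = 76.3%, against 76% stated

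The figure therefore assumes that all six weekly scores are observed. If 10% or 20% of one oxybutynin arm gave no scores at all, the same formula gives 74.3% or 71.9%. These losses are upper bounds, because scores recorded before stopping still count. Power is not the main issue.

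**4. Possible bias, illustration only.** Let p be the share stopping in the oxybutynin (A) or placebo (P) group. Let L be the points by which stoppers' week-6 reduction falls short of completers' (negative if they do better). If stopping is unrelated to earlier scores, the missing-at-random estimate exceeds the all-randomized difference by

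bias = pA × LA - pP × LP.

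Section 1.2 reports mean reductions in women of 16.9 (5.0 mg), 10.6 (2.5 mg) and 5.7 (placebo), so D = 11.2 and 4.9. The stopping counts and the values of L are assumptions.

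| Case | 1 of 26 | 3 of 26 | 5 of 26 |
|---|---|---|---|
| High dose, all benefit lost (LA = 11.2) | +0.43 | +1.29 | +2.15 |
| High dose, half lost (LA = 5.6) | +0.22 | +0.65 | +1.08 |
| Stoppers follow completers (LA = 0) | 0 | 0 | 0 |
| High-dose stoppers gain 5.6 on other therapy | -0.22 | -0.65 | -1.08 |
| Placebo stoppers gain 5.6 on other therapy | +0.22 | +0.65 | +1.08 |
| Low dose, all benefit lost (LA = 4.9) | +0.19 | +0.57 | +0.94 |

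Equal numbers of stoppers in both groups with the same L cancel.

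For scale, section 1.2's SDs with 26 per group give these 90% half-widths, using t = 1.676 on 50 df:
- high dose: sqrt((15.6² + 10.2²)/26) = 3.66, half-width 6.13
- low dose: sqrt((7.7² + 10.2²)/26) = 2.51, half-width 4.20

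The full-loss cases are 7%, 21% and 35% of the half-width for the high dose, and 4%, 13% and 22% for the low dose.

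**The case against.** The two paragraphs of section 12.3.2 can largely be read together. The toxicity paragraph encourages and permits, it does not order, and its off-study date accepts data recorded after the last dose. A site can follow the general rule and keep the exit for a man who will not go on. That stands, and it places the binding conflict in section 8.2, whose last step is directive. Calling the toxicity paragraph a specific exception works less well: it is not marked as one, and the general rule covers every reason for stopping.

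The low-dose row's silence on questionnaires is partly filled by the toxicity paragraph, which makes the request at either dose. That also stands. The row still orders study exit.

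The numbers affected may be small. Section 8.2 puts one reduction step (low dose) or two (high dose) before the exit, and section 1.2 reports no difference in discontinuation in women. The responder analyses do not rely on missing-at-random. All of this limits the likely effect, but it neither removes the contradiction nor repairs the primary contrast.

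A reader might infer that the primary result will be biased in favour of oxybutynin, or that every man with toxicity must be dropped. The documents support neither. They give no stopping rate for this trial and nothing on how scores move after stopping, and the exit is mandatory only at the last step of section 8.2.

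**Conclusion.** The contradiction is certain on the text and should be fixed. Section 8.2 ends data collection at a point where the opening of section 12.3.2, and plausibly section 12.4, continue it. The toxicity paragraph and Appendix VII lean towards ending it.

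The consequence is possible, not established: some week-6 diaries may not be collected, and for those men the primary contrast would depend on missing-at-random. Bias could be positive, zero or negative. The illustrative range of -1.1 to +2.2 points rests on assumed stopping counts, assumed courses after stopping, and effects and SDs from women. It is not a prediction.

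**What to change.** For data collection only, with no change to any dosing or treatment-stopping rule:

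- Reconcile section 8.2, the toxicity paragraph of 12.3.2 and the early-stop note in Appendix VII with the opening of 12.3.2 and section 12.4, by separating off treatment from off study. A man who stops study drug continues the diary and weekly booklets through Day 49 unless he withdraws from data collection.
- Align the diary and weekly column headings in section 5.0 and the description in section 11.3, so that they cover men no longer on drug. Give Day 49 as the end point in section 12.3.2.
- State in section 13.4 that scores recorded after stopping drug enter the primary mixed model. Intent-to-treat implies this, but the section does not say it.
- Record other hot-flash treatment through the item on medication changes already on the Appendix VII call form.

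The cost is a wording amendment; booklets and weekly calls through Day 49 are already planned. The burden on these men is under a minute a day for the diary (11.3) and 10-15 minutes a week for the Symptom Experience Questionnaire (11.4), plus the short IPSS and HFRDIS forms. Some later scores may reflect other therapy. Section 8.1.1 says "Patients should not receive any other treatment or participate in trials which would be considered treatment for hot flashes or impact the primary endpoint", so the sponsor must state how that applies to men who are off drug but still giving data; this review proposes no rule for it.

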#### 12.4 Extraordinary Medical Circumstances

If, at any time the constraints of this protocol are detrimental to the patient's health and/or the patient no longer wishes to continue protocol therapy, protocol therapy shall be discontinued. In this event:

- Document the reason(s) for discontinuation of therapy on data forms.
- Follow the patient for protocol endpoints as required by the Study Calendar.

## 12.5 Managing ineligible patients and registered patients who never receive protocol intervention

#### **Definition of ineligible patient**

A study participant who is registered to the trial but does not meet all of the eligibility criteria is deemed to be ineligible.

#### Follow-up for ineligible patients who continue with protocol treatment

Patients who are deemed ineligible after registering may continue protocol treatment, provided the treating physician, study chair, and executive officer agree there are no safety concerns if the patient continues protocol treatment. All scans, tests, and data submission are to continue as if the patient were eligible. Notification of the local IRB may be necessary per local IRB policies.

